****CONFIDENTIAL & PROPRIETARY****

List of Abbreviations and Definition of Terms

AE	Adverse Events
BPH	Benign Prostatic Hyperplasia
BRB	Biomedical Research Building
CNS	Central Nervous System
CRF	Case Report Form
CTCAE	Common Terminology Criteria for Adverse Events
eCRF	Electronic Case Report Form
ED	Erectile Dysfunction
EDITS	Erectile Dysfunction Inventory of Treatment Satisfaction
EDV	End Diastolic Velocity
GCP	Good Clinical Practice
HIPAA	Health Information Portability and Accountability Act
ICF	Informed Consent Form
ICH	International Conference of Harmonization
ICI	Intracavernosal Injection
IEC	Institutional Ethics Committee
IIEF	International Index of Erectile Function
IIEF-EF	Erectile Function Subdomain Score
IRB	Institutional Review Board
ISCI	Interdisciplinary Stem Cell Institute
MCID	Minimal Clinically Important Difference
mL	Milliliter
ng/dL	Nanograms Per Deciliter
PDE5i	Phosphodiesterase 5 inhibitor
PPP	Platelet Poor Plasma
PRFM	Platelet Rich Fibrin Matrix
PRP	Platelet Rich Plasma
PSV	Peak Systolic Velocity
RCT	Randomized Controlled Trial
SAE	Serious Adverse Events
SEP3	Sexual Encounter Profile
SOP	Standard Operating Procedure
SWT	Low-intensity Shockwave Therapy
TE-SAE	Treatment Emergent Serious Adverse Events
UM	University of Miami
VAS	Visual Analogue Pain Scale

Protocol Synopsis						
TITLE	COMBINING SHOCKWAVE THERAPY AND PLATELET RICH PLASMA FOR TREATING ERECTILE DYSFUNCTION IN DIABETIC MEN (COCKTAIL-DM)					
SPONSOR	Jniversity of Miami, Miller School of Medicine - Department of Urology					
PHASE OF STUDY	Phase I/II					
STUDY THERAPY	Autologous Platelet-Rich Plasma (PRP) + Low-intensity Shockwave Therapy (SWT)					
STUDY DESIGN	Single arm, Open Label, Pilot Trial					
ROUTE OF ADMINISTRATION	Intracavernosal Injection (PRP) + extracorporeal shockwave therapy (SWT)					
SUBJECT POPULATION	15 male subjects between the age of 30-80 with Mild or Mild-to-Moderate ED and controlled Diabetes Mellitus (DM)					
STUDY	Primary: To investigate biochemical markers of neo-angiogenesis in patients before and after PRP injection + SWT					
OBJECTIVES	Secondary: To study efficacy and incidence of adverse events and safety of PRP injection + SWT treatment in men with mild-moderate ED, as measured by IIEF.					
	15 men with Erectile Dysfunction (ED) of organic origin and Diabetes (Type 1 or Type 2), that meet all of the inclusion and none of the exclusion criteria, will be enrolled and will receive PRP+SWT.					
INVESTIGATION PLAN	Autologous PRP injection + SWT therapy. All subjects in this group will receive 2 sessions of autologous PRP penile injection with 30 ± 7 day treatment interval. 5mL of PRP will be injected at each session. Additionally, patients will receive a total of 3600 shocks over a five-week period, starting at initial PRP injection.					
DURATION OF STUDY	7 months (1 month screening, 5 weeks of therapy sessions, 6 months of follow-up).					
DEFINITION OF ENDPOINTS	 Primary: Changes in markers of vasodilation (eNOS, nNOS), neo-angiogenesis (VEGF, CD-31), and systemic markers of endothelial function (EPCs, SDF-1α, and SCF). Secondary: Differences in Doppler ultrasound parameters (PSV and EDV) from baseline to 6 months post-therapy. Treatment satisfaction as assessed by EDITS questionnaire in all subjects. Incidence of Serious Adverse Events experienced up to 6 months post-therapy. 					
	 Exploratory: Change in IIEF-EF score from baseline to 3 and 6 months post-therapy. Percentage of subjects that achieve minimal clinically important difference (MCID) in IIEF-EF from baseline to 3 and 6 months post-therapy. Percentage of subjects who either decrease or discontinue use of PDE5i after three months post-therapy 					

Protocol Synopsis							
	1. Be Male						
	2. Be 30 to 80 years of age (inclusive).						
	3. Be able to provide written informed consent.						
INCLUSION	 Have a diagnosis of mild to moderate ED (12-21) or mild ED (22-25) based on IIEF-EF questionnaire score. 						
CRITERIA	 Have diagnosis of Diabetes Mellitus (Type 1 or Type 2), as documented by history of Hemoglobin A1C > 7% OR on medical therapy for Diabetes. 						
	6. Be in a stable relationship and have a minimum of 2 sexual attempts per month for at least one month prior to enrollment.						
	7. Agree to comply with all study related tests/procedures.						
	 Previous penile surgery of any kind (except circumcision and condyloma removal), such as penile lengthening, penile cancer surgery, penile plication, grafting. 						
	 Previous history of priapism, penile fracture, Peyronie's Disease, or penile curvature that negatively influences sexual activity, 						
	 Abnormal morning serum testosterone level defined as a value lower than 300 ng/dL (±5%). 						
	4. Psychogenic ED as determined by study investigator.						
EXCLUSION	5. Patients using ICI for management of ED						
CRITERIA	Patients with generalized polyneuropathy, neurological conditions, or psychiatric disease (such as bipolar disorder or depression).						
	 Have a serious comorbid illness or condition that, in the opinion of the investigator, may compromise the safety or compliance of the subject or preclude successful completion of the study. 						
	 History of consistent treatment failure with PDE5 inhibitors for therapy of ED. 						
	9. Poorly controlled diabetes as indicated by Hemoglobin a1c > 7.5%.						
	10. Use of antiplatelet medication						

Protocol Title

COMBINING SHOCKWAVE THERAPY AND PLATELET RICH PLASMA FOR TREATING ERECTILE DYSFUNCTION IN DIABETIC MEN (COCKTAIL-DM)

1. Background

1.1 Platelet-based therapies

Platelet-derived therapies are a growing trend across multiple medical and surgical specialties including dermatology, ophthalmology, cardiology, colorectal surgery, plastic surgery and mainly orthopedics [1-2]. One of the most well described platelet-based therapies is autologous platelet-rich plasma (PRP) [3]. PRP is derived from the centrifugation of whole blood with a separator gel to remove the red and white blood cells. The resulting supernatant has a greater than four-fold increase in platelets and other plasma proteins [1]. This concentrate is then administered via injection. PRP has been frequently used for orthopedic conditions such as bone and soft tissue trauma, inflammatory conditions, and chronic pain syndromes [3-4]. Evidence suggests that platelets play an important role not only in coagulation but also in regulation of body metabolism, promotion of the wound healing, tissue regeneration, vascular remodeling and inflammatory/immune responses through secretion of growth factors, cytokines and chemokines [4-5]. These biologically active proteins include transforming growth factorβ, platelet-derived growth factor, platelet-derived epithelial growth factor, insulin- like growth factor, vascular endothelial growth factor, basic fibroblast growth factor, as well as many others [6]. When platelets are activated, they release these growth differentiation factors, facilitating even nerve repair and regeneration [7-8]. Growth factors act locally and are implicated in many aspects of natural wound healing, including chemotaxis, cell proliferation, cell differentiation and angiogenesis. They also control and conduct synthesis, modification and degeneration of extracellular matrix proteins. Coordination of these cellular and molecular processes is integral to proper wound healing and tissue regeneration [9]. The key role of platelets in these processes makes them an attractive candidate for therapies aimed at accelerating natural healing, as well as tissue regeneration.

Autologous blood-based biomaterials are promising therapeutic options for varied pathology. Rapid generation of therapeutic material following collection allows for pointof- care therapy [10]. Furthermore, anautologous therapy avoids the need for immunosuppression and eliminates concerns of rejection. Newer strategies to prolong the anti-inflammatory and wound healing properties of platelets have focused on creating a fibrin matrix (platelet rich fibrin matrix, PRFM) to bind the platelets and prevent extravasation from the site of injection, thereby addressing the concern of early washout with PRP [11]. In addition, PRFM offers a potential scaffold for tissue ingrowth and may allow continued release of platelet-related factors for a longer duration. Across multiple disciplines, PRP has been used both as a primary treatment modality and as a supplement to other therapies in hopes of supplementing wound healing, tissue regeneration, and angiogenesis. Although most of the studies focusing on PRP injections have been relatively small and heterogenous, they largely support the concept of administration in terms of safety, while efficacy remains uncertain. Finally, the concept of

autologous therapy has be shown in the real world that it is particularly attractive to patients [10].

1.2 Platelet-rich plasma treatment for erectile dysfunction

Erectile dysfunction (ED) affects as many as 1 in 4 men, and evidence indicates that incidence is rising [12-13]. The pathophysiology is multifactorial, but the most common pathophysiology, vasculogenic erectile dysfunction, has as first sign endothelial dysfunction secondary to inflammation [14]. The most common treatments for ED aim to improve endothelial function through augmentation of the nitric oxide pathway [15]. Return of potency after surgical injury of CNS partially depends on axon regeneration in the remaining neural tissue [16]. The process of regeneration and functional recovery of peripheral nerve is slow and is influenced by many factors [17] such as extracellular matrix, neurotrophic factors, and cellular components [18]. Recent advances in the understanding of molecular pathways and their physiological role demonstrate that growth factors are an important part of the development, maintenance, and regeneration of the nervous system [19]. Various growth factor neuromodulatory strategies, including insulin-like growth factor (IGF-I) and neurotrophic factors, are investigated to identify agents that may have neuroprotective and regenerative function after the occurrence of peripheral nerve injury. Accumulating evidence indicates that neuroimmunophilin ligand (such as FK506) plays a significant role in neural regeneration and upregulation of neuronal nitric oxide synthase (nNOS), as well as in the recovery of erectile function after CN injury occurrence [20-21]. FK506 neuroprotection after CN injury is mediated by antioxidative/nitrosative and anti- apoptotic pathway [22]. When platelets are activated, they release many kinds of growth differentiation factors and a few types have been found to facilitate nerve repair and regeneration. Moreover, corporeal dysfunction due to smooth muscle atrophy or other inracavernosal pathology can lead to corporo-venous occlusive erectile dysfunction despite a normal arterial inflow. Rejuvenating the Corporeal tissues with PRP, which is well known for its growth and healing factors, is a possible modality as a potential treatment for erectile dysfunction according to Alkhayal et al [23]. In their retrospective study examining the efficacy of one intra-cavernosal PRP injection to 40 ED patients, they reported that mean IIEF-5 score before treatment was 13 (5-20) and post treatment IIEF-5 = 17 (7-24), (p < 0.001). Other studies have shown similar results with minimal side effects, no serious adverse reactions and potential efficacy (Table 1) [23-26].

****CONFIDENTIAL & PROPRIETARY****

	Human Studies of PRP for ED							
Author	Year	Number of Patients	Patient Population	Administration	Followup	Adverse Events	Conclusion	
Banno [26]	2017	N=9	Penile Rehab	PRP ICI into Pnies with Vacuum Device	4 weeks	No AEs reported	PRP may represent a safe and viable option as a supplementary therapy for penile rehabilitation. Particularly notable is the prospect of zero side effects.	
Matz [24]	2018	N=16	Erectile dysfunction, Peyronies Disease	PRP with CaCl ICI	15.5m	Minor: Bruising 1, Mild Pain 4. Major: none	PRFM injections for ED, PD, and female SUI are feasible and safe. Although the limited data is suggestive of efficacy, a placebo control will be required in subsequent efforts for confirmation	
Epifanova [25]	2019	N=10	Erectile Dysfunction	6 injections PRP with CaCl2 ans Shockwave	60 Days	No AEs reported	There were no serious adverse events as well as severe adverse events. Erectile dysfunction symptoms in all men participated in the study significantly decreased after treatment with PRP-therapy and extracorporeal shockwave therapy	
Alkhayal [23]	2018	N=40	Erectile Dysfunction	1 injection PRP	>1 month	No AEs reported	Platelet rich plasma is a safe and efficacious option for penile rejuvination and improvement of erectle dysfunction	

Table 1: Summary of published studies and abstracts

To date, there are no treatments that address the underlying cause of endothelial dysfunction, although LIST treatment for ED has shown promising results. Plateletderived therapies targeting inflammation and promoting tissue/nerve regeneration and may represent a potential treatment option towards this direction. Despite growing evidence to the efficacy of PRP, no randomized placebo-controlled studies exist.

1.3 Energy-based treatments for erectile dysfunction

Shockwave therapy has been utilized by urologists for other ailments, such as treatment of kidney stones through a non-invasive manner. Interest in the use of low-intensity shockwave therapy for erectile dysfunction was augmented with success seen in preclinical models. The hypothesis for SWT's mechanistic actions is neo-angiogenesis, recruitment of progenitor cells and resident stem cells, improvement of microcirculation, vasodilation with subsequent increase in nitric oxide, decrease in fibrosis, and nerve regeneration. There have been 13 published clinical studies regarding use of SWT for ED. Multiple systematic reviews and meta-analyses have been performed for SWT for ED, and there is consensus that SWT shows promise in the treatment for ED.

1.4 Combination Restorative Therapy for Erectile Dysfunction

The development of ED therapeutics that focus on neurovascular regeneration and repair strategies are of great importance. A large body of *pre-clinical* work has demonstrated the effect of SWT alone (monotherapy) on angiogenesis and progenitor / stem cell recruitment for ED [2, 3, 8-11]. PRP monotherapy importantly is also supported by well-defined mechanistic insights obtained from rigorously conducted animal studies [12-19]. All the previous studies in humans have evaluated either IIEF scores and / or penile Doppler ultrasound hemodynamic parameters, but there has not been evaluation of the treatment as a combination. The proposed mechanisms of both interventions would

suggest that the combination therapy would act in a synergistic manner, with superiority over monotherapy. Success of our proposed work could fundamentally change the standard of care for ED and substantially improve the quality of life for tens of millions of men.

2. Study Objectives

2.1 Primary Objective:

To investigate of the underlying mechanisms of PRP and SWT in men with mild-moderate ED and Diabetes.

Exploratory:

- Change in IIEF-EF score from baseline to 3 and 6 months post-therapy.
- Percentage of subjects that achieve minimal clinically important difference (MCID) in IIEF-EF from baseline to 3 and 6 months post-therapy.
- Percentage of subjects who either decrease or discontinue use of PDE5i after three months post-therapy

2.2 Secondary Objective:

To study the treatment safety and efficacy of PRP and SWT treatment in men with mildmoderate ED and Diabetes.

3. Study Endpoints

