3.1 Primary Endpoints

- Changes in markers of vasodilation (eNOS, nNOS), neo-angiogenesis (VEGF, CD-31), and systemic markers of endothelial function (EPCs, SDF-1α, and SCF).

3.2 Secondary Endpoints (efficacy):

- Differences in Doppler ultrasound parameters (PSV and EDV) from baseline to 6 months post-therapy.
- Treatment satisfaction as assessed by EDITS questionnaire in all subjects.
- Incidence of Serious Adverse Events experienced up to 6 months post-therapy.

3.3 Exploratory Endpoints:

- Change in IIEF-EF score from baseline to 3 and 6 months post-therapy.
- Percentage of subjects that achieve minimal clinically important difference (MCID) in IIEF-EF from baseline to 3 and 6 months post-therapy.
- Percentage of subjects who either decrease or discontinue use of PDE5i after three months post-therapy

4. Study Location

The study will be funded by the CTSI pilot award (GR019191) and coordinated by the University of Miami (UM), Miller School of Medicine, Desai Sethi Urology Institute. All

study visits will take place in the Department of Urology clinics, (PAC: [name], University of Miami Miller School of medicine, Miami, FL. & Lennar: [name]) PRP preparation and SWT therapy administration will take place in the PAC andrology lab and clinic.

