12.1 Data Analysis Plan

Analysis plan: Continuous data will be analyzed using ANOVA with repeated measures, or student's T-Test (where applicable) in order to compare differences between the treatment and control groups. For categorical data, Fisher's Exact test to determine differences between groups. Statistical significance will be evaluated using α =0.05.

13. Risks and Benefits

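### The mechanistic primary objective in section 2.1 goes beyond the synopsis objective, and the single-arm design, endpoints and analysis plan cannot support it

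*Combined protocol and SAP*

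**What the plan says.** The primary objective is worded in two ways. Section 2.1 has "To investigate of the underlying mechanisms of PRP and SWT in men with mild-moderate ED and Diabetes". The Study Objectives row of the synopsis has "To investigate biochemical markers of neo-angiogenesis in patients before and after PRP injection + SWT".

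The primary endpoint in section 3.1 reads "Changes in markers of vasodilation (eNOS, nNOS), neo-angiogenesis (VEGF, CD-31), and systemic markers of endothelial function", the last group being EPCs, SDF-1α and SCF. That makes seven markers, with no expected direction and no time point. Clinical response is listed apart from the markers: "Differences in Doppler ultrasound parameters (PSV and EDV) from baseline to 6 months post-therapy" is secondary (3.2) and "Change in IIEF-EF score from baseline to 3 and 6 months post-therapy" is exploratory (3.3).

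Section 12.1 is the whole analysis plan. It names repeated-measures ANOVA or a t-test for continuous data and Fisher's exact test for categorical data, "in order to compare differences between the treatment and control groups", at α = 0.05. The synopsis describes a single-arm, open-label pilot in 15 men, all of whom receive both PRP and SWT.

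**The concern.** An objective about mechanism asks whether the treatment acts through the marker. The plan measures whether markers change and, separately, whether erectile function or penile blood flow changes. It contains no step that joins the two.

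The two wordings also set different standards for success. Under the synopsis, a before/after description of the markers completes the primary objective. Under section 2.1 it does not, and no planned analysis could complete it. If 2.1 stands, the trial either falls short of its own primary objective or invites a conclusion stronger than its data allow.

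**Working it through.** The documents give no power, effect size or SD for any marker, so there is no stated figure to reproduce. The check is a reading of the plan, followed by arithmetic for scale.

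**1. Objective against plan**

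| Needed for a mechanism objective | What the plan has |
|---|---|
| One agreed objective | Mechanism in 2.1; markers before and after in the synopsis |
| Predicted sign per marker | None in 3.1; section 1.3 gives pathways for SWT only, including "recruitment of progenitor cells and resident stem cells" |
| Analysis linking marker to response | None in 12.1 |
| A comparison that isolates the treatment | Single arm; 12.1 refers to a control group that does not exist |
| Separation of PRP from SWT | None; every man receives both |

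**2. Data available for a link.** The schedule in section 7.1 has EPC-CFU and IIEF at Screening, Month 3 and Month 6, and Doppler at Screening and Month 6, in the same men. EPC-CFU is the only 3.1 marker with a described and scheduled assay. Section 7.2.10 stores plasma for later use. Brachial FMD is scheduled at the same three visits as EPC-CFU but is not a 3.1 endpoint.

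**3. Why two mean changes do not make a link.** A paired test uses t = mean(d) / (s_d/√n), where d is the change in that one measure. The correlation between a man's marker change and his IIEF-EF change does not enter either test. Illustration with assumed effects: if marker and IIEF-EF each truly change by 0.6, 0.8 or 1.0 SD but are unrelated across men, the power of each paired test at n = 15 (two-sided 0.05) is 0.58, 0.82 or 0.95. Both are then significant with probability 0.58² = 0.34, 0.82² = 0.67 or 0.95² = 0.90. Joint significance is common with no link at all.

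**4. What an association could deliver at n = 15.** Assume 15 complete pairs, two-sided α of 0.05 and the Fisher z approximation for a simple Pearson correlation, with SE = 1/√(15 − 3) = 0.289.
- CI around r = 0: ±tanh(1.96 × 0.289) = ±tanh(0.566) = ±0.51.
- CI for an observed r = 0.5: tanh(0.549 ± 0.566) = −0.02 to 0.81.
- True r needed for 80% power: tanh((1.960 + 0.842)/√12) = tanh(0.809) = 0.67.
- Power = Φ(√12 × atanh(r) − 1.96): about 19% at r = 0.3, 48% at r = 0.5 and 85% at r = 0.7.
- With 12 complete pairs (assumed), the r needed for 80% power rises to tanh(2.802/√9) = 0.73.

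**5. What limits even a clear association.** Section 7.2.6 allows a baseline IIEF up to 6 months old, and section 7.2.5 a Doppler result up to 12 months old, so clinical and marker baselines may differ in date. Section 5 describes the men as regular PDE5i users, whereas section 7.2.14 has them stop for the study, so PDE5i use may differ between baseline and follow-up. Time trends and regression to the mean have no control group to absorb them.

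**The case against.** The strongest reply is that this is only a wording mismatch. Section 2.1 says investigate, not demonstrate. The trial is labelled a pilot, and the synopsis already carries the modest aim. Once 2.1 is reworded, no mechanistic objective remains for a linking analysis to serve. Most of this stands: rewording is the main remedy and the association is optional. It does not remove the conflict between the two primary objectives.

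It is also fair that correlation is not a decisive test of mechanism. If men respond alike, a true mediator can show r near 0.

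A reader might infer several stronger points that the documents do not support:
- **A contradiction over EPCs**, on the view that recruitment to tissue lowers circulating cells while better endothelial function raises them. No section says that recruitment lowers circulating EPCs or that a rise is favourable. What is missing is a stated sign.
- **A 67% risk of a false mechanism claim.** That figure is the product of two assumed powers when both effects are real. It is not an error rate.
- **That the sponsor will report mechanism.** No section says so.
- **That EPC-CFU is the only vascular measure scheduled.** Brachial FMD is also scheduled.

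**Conclusion.** The point holds as a conflict between objectives and a limit on the conclusion. Section 2.1 sets a primary objective that differs from the synopsis and that the design, the endpoints and section 12.1 cannot meet. What the trial can support is a description of marker change from before to after combined treatment.

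The conflict and the missing link are read directly from the text and need no assumption. The precision figures assume complete pairs, a two-sided 0.05 level and a simple correlation. On that basis about 30 men would be needed for 80% power at r = 0.5 and about 85 at r = 0.3, so 15 men can give only an imprecise estimate.

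It may be tempting to allow the word mechanism whenever a marker moves in a predicted direction and correlates with response. The documents do not support such a rule. With one arm, both therapies given together, a possible change in PDE5i use and possibly old clinical baselines, agreement of sign and association would still not attribute the effect to PRP, to SWT or to their combination.

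**What to change.** 1. Reword section 2.1 to the synopsis's descriptive aim: to describe the change in markers from before to after PRP + SWT. Use the same words in both places and make them cover all the marker groups in 3.1.
2. State that the primary conclusion is limited to marker change, with no claim of mechanism. Section 12.1 needs a before/after analysis to match, in place of its comparison with a control group.
3. Optionally, add to 12.1 one estimation-only association across men: change in EPC-CFU with change in IIEF-EF, and with change in PSV at Month 6. Spearman correlation or regression with a 95% CI would do. Label it hypothesis-generating, and attach no rule that turns the result into a mechanism claim.
4. If it is added, state beside it that at n = 15 the CI is about ±0.5 around r = 0, and that the dates of baseline IIEF and Doppler and the change in PDE5i use limit interpretation. Sections 5 and 7.2.14 must be reconciled on PDE5i use.

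The cost is a few sentences and, if chosen, one analysis of data already scheduled, with no new visits, samples or men. The downside is a less ambitious objective and an imprecise association estimate.
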